7. DATA MANAGEMENT AND DATA PROTECTION

Concerning the data-management, the treatment, communication, and transfer of personal data of all participants will be adjusted in compliance with EU Regulation 2016/679 of the European Parliament and the Council of April 2, 2016 related to the people physical protection with regards to the processing of personal data and the free circulation of data, being binding as of May 25, 2018. All data analysis will be conducted on pseudo-anonymized data and no personal data or data that could potentially identify an individual will be included in the final report.

Data extraction. The data extraction process will be performed according to the principles established by the healthcare services, including the data protection policies in this regard. All processing of patients' personal data collected within the study will be conducted according to conventional confidentiality.

Data processing and management. Migrants who will participate in the focus groups of the study will be invited in a visit or by telephone by their own doctor or they will be recruited through civil society organizations working with migrant populations, and they will sign the consent form on the day of the FGs.

They will be requested to answer some questions related to socio-demographic data (i.e., sex, age, or country of birth among others, see document 'Information of the Patient' attached) with a statistical purpose of the analysis of the participants of the FG. No name or personal data will be registered. The questionnaire will be identified with a code and only researchers from the study will have access to these data.

The qualitative study data will be obtained through the informed consents of the participants, in accordance with the provisions of articles 6.1 a) and 9.2 a) of the RGPD. Digital audio recordings will be stored and secured in the local server of ISGlobal (VPN), where only participating investigators will have access to it. These will be erased after five years of completion of the study. No international data transfer will take place of the recordings made in the FG discussions.

Transcriptions of the audios and questionnaires will be stored in ISGlobal's VPN and only participating investigators will have access to the database, and integrity and security of data will be maintained. In addition, a password will be requested to all researchers in order to access the data, registering any access. Also, a regular backup will be generated to avoid loss of information. An adequate documentation of data (metadata) -i.e., adding semantic descriptions, annotations, etc. will facilitate identification and support the effective reuse of research data. Only encrypted data will be transferred to third parties and other countries, which in no case will contain information that can directly identify the participant (such as name, initials, address, social security number, etc.). In the event of such a transfer, it would be for the same purpose of the study described and would guarantee confidentiality.

In addition to the rights already provided for in the previous legislation (access, modification, opposition and cancellation of data, deletion in the new Regulation) participants can also limit the processing of data collected for the project that are incorrect, request a copy or be transferred to a third party (portability). In order to exercise these rights, the participants must contact the principal investigator of the study or the Data Protection Officer of ISGlobal via [contact]. Participants from the Catalan Institute of Health must contact the Data Protection Officer via [contact]. Also, the participants have the right to contact the Data Protection Agency if they remain unsatisfied.

ISMiHealth protocol version 8.0, October 10, 2024

This project does not prevent advanced data usage. In accordance with the provisions of article 35 of the RGPD, the project does not meet the necessary characteristics that require the performance of an impact assessment.

Reutilization of data First, a standardized communications protocol to retrieve (meta) data by their identifier, free and universally implementable, will be generated, including a clear and accessible data usage license. After 10 years, all data will be eliminated and destroyed.

Data will be anonymously uploaded in the repository, and those records that may lead to the individual identification of the participants will be removed or grouped with the aim of keeping their identity hidden at all times. Likewise, the possibility of withdrawing all the individual information of a patient will be guaranteed when so expressed. The data will be stored in a repository created specifically for this purpose in the ISGlobal data centre in the Campus Mar ([name]), which requires prior appointment with IT staff and therefore only those responsible for computer security and researchers linked to the project will have access to them. A series of protocols are in place to test and maintain network security, and to provide access management policies for network drives, databases, and remote access. The system is protected from power interruptions, with controlled access to authorized users only.

The study does not involve biological samples.

8. FUNDING

The ISMiHealth project received funding (87.120,00€) from the Health Research Fund Call 2021 of The Ministry of Science and Innovation to support this study economically. Study investigators will not receive any personal compensation or extra salary for participating in this study.

9. RESULTS COMMUNICATION

The promoter and investigators commit to publish the results of the study in journal articles, other scientific publications and communications to congresses. Authorship in case of publication will be decided according to quantitative and qualitative input to the study. The principal investigator will be the first or last author of the articles.

Annex 6. Online questionnaire

QUESTIONNAIRE 1: MIGRANT INDICATORS IN HEALTH INFORMATION SYSTEM

Background information
My name is and I am a medical student at the University of Barcelona. I ar
currently working on my MSc thesis project on "The perception of migrant populations about health dat
collection in Catalonia". This project is supported by the study group for Infections in Travellers an
Migrants (ESGITM) of the European Society of Clinical Microbiology and Infectious Diseases (ESCMID
and coordinated by [name], researcher at the Barcelona Institute for Global Healt
(ISGlobal) in Barcelona.
The aim of this project is to explore what type of migrant indicators are routinely collected or registere
in the health information systems at primary care level in European countries.
For this purpose, we have developed a short online survey. The survey contains questions regarding th
health information systems in your country and will not take more than 2 minutes to be completed
Additional information about the study can be found in the attached Study Protocol.
We would greatly appreciate if we could have a couple of minutes of your time to answer this short
survey.
Many thanks for your time.
Profile information:
1. Name
2. Profession
Primary Care doctor
Specialist
Primary Care nurse
Other
3. Type of primary care centre
Rural Urban
Public Private
Health centre Migrant examination centre
4. Name of the Centre
5. City, county
6. Country
Questionnaire:
1. Does you centre/hospital have a digital electronic patient record (EPR) system?
YES
NO
2. How is this EPR implemented in your country?
Country level (the same EPR for the whole country)
Regional/county/state level
Local level

3. Is this EPR system manually registering socio-demographic information for new users?

	Yes, No, it is imported from another database containing demographic information
4.	Is there any migrant indicator regarding the origin routinely registered in the EPR? YES NO
5.	What type of indicators are included (multiple options available)? Migrant /non-migrants Country of birth Nationality
6.	Are there any other migrant indicators collected? YES NO
7.	What type of indicators? Type of migrant: Asylum seeker/refugeed/labour migrant), Last country of residence Date of arrival to the country Language Need of interpreter
8.	What other migrant indicators are included?

ISMiHealth protocol version 8.0, October 10, 2024

9. If you have any comment or suggestion, we would be glad to hear from you:

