3. OBJECTIVES

The aim of this study is to better understand the needs, insights and comfortableness of migrants around the collection of data in healthcare centres in order to be able to improve the process of data collection and care.

Specific objectives:

Aim 1: Identify the main migrant health indicators routinely registered in the electronic patient record systems of European countries, including those indicators for addressing the vulnerabilities of migrant populations.

Aim 2: Assess the perception of migrant and refugee populations in Catalonia about the health data that is collected in terms of quantity, quality, and usefulness but also in terms of respect to human integrity, protection of human rights, or discriminatory aspects.

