4. STUDY DESIGN

The sub-study will be developed parallel to the overall project, including the following stages:

- **I. A literature review** and analysis of the migrant health indicators used in the health information systems including those indicators for addressing the vulnerabilities of migrant populations.
- **II.** A survey among health professionals from different European countries to inquire about the variables and indicators that are collected and registered in the electronic patient record (EPR) system.

The survey will be distributed to healthcare providers at primary care level and specialists through the network of the Study Group on Infections in Travellers and Migrants of the European Society of Clinical Microbiology and Infectious Diseases (ESCMID). Candidates will receive the invitation to participate via an online link to the survey, designed on LimeSurvey platform, and their access to it will represent their consent to participate.

The survey will include some profile information of the individual and their workplace, followed by several questions regarding the presence and features of the digital EPR systems, the migrant indicators that are routinely collected in the health information systems, the data protection policy regarding these indicators and the possibility of linking these data with other datasets containing migrant indicators (See Annex 6).

III. A qualitative research study to assess their perception on the data collection process, whether or not they feel comfortable about disclosing sensitive variables (such as country of birth, time of arrival in the host country, legal status, reason for migration, ever resided abroad, or sociodemographic data) and perceived stigma around it. This will be carried out through the organization of 26 focus group (FG) discussions with migrant populations, of an estimated maximum of 10 people each. 4 FGs will be held in Spanish (2 with males and 2 with females), 4 will be held in French (2 males and 2 females), 4 in English (2 males and 2 females), 2 in Russian (1 males and 1 females), 2 in Malayalam (1 males and 1 females), and 10 in Arabic (5 males and 5 females).

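### The Annex 6 survey cannot show which kind of patient record an answer describes, nor tell a NO from a lack of knowledge, and its target population is stated inconsistently

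*Protocol*

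**What the plan says.** The survey belongs to the Health Data Collection sub-study of the protocol (Annex 6). Four places define it.

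- **Sub-study section 3, Objectives, Aim 1:** "Identify the main migrant health indicators routinely registered in the electronic patient record systems of European countries". This has no restriction to primary care.
- **Sub-study section 4, Study design, stage II:** "The survey will be distributed to healthcare providers at primary care level and specialists". The route is the network of an infectious-disease society's study group.
- **Online questionnaire, introduction and items:** the introduction gives the scope as "in the health information systems at primary care level in European countries". Profile item 2 lists primary care doctor, specialist, primary care nurse and other. Profile item 3 is "Type of primary care centre"; its choices are rural or urban, public or private, and "Health centre Migrant examination centre". Item 1 asks "Does you centre/hospital have a digital electronic patient record (EPR) system". Item 2 asks "How is this EPR implemented in your country" and offers three administrative levels. Item 3 asks whether socio-demographic data are entered manually or imported. Item 4 reads "Is there any migrant indicator regarding the origin routinely registered in the EPR? YES NO". Item 6 is also YES or NO. Item 9 is a free comment.
- **Sub-study section 5, Data analysis:** survey data will be summarised in Stata with frequencies and inferential statistics. It gives no rule on setting or on uncertain answers.

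**The concern.** A survey meant to list what record systems register needs two things from each reply: which system it describes, and whether the respondent knows. This form secures neither.

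A hospital specialist who answers item 1 as worded describes a hospital EPR. Items 2 to 4 then refer back to that same EPR. The setting item gives this person nothing suitable to tick. A clinician who never sees the registration step has no way to say so in items 2, 3, 4 or 6.

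At stake is how the survey's descriptive result can be read. If a table reports how often country of birth or date of arrival is registered, the reader will not know whether it describes primary care, hospitals or both. Nor will the reader know how many of the NO answers are informed ones.

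**Working it through.** The documents give no sample size, response rate or expected frequency for this survey. There is therefore no figure to reproduce, and the check is a comparison of texts.

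**Step 1. Target, respondents and unit asked about.**

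| Element | Where | Scope |
|---|---|---|
| Aim | Sub-study section 3, Aim 1 | EPR systems generally |
| Aim | Questionnaire introduction | Primary care level only |
| Respondents | Sub-study section 4, stage II | Primary care and specialists |
| Unit asked about | Questionnaire item 1 | Centre or hospital |
| Setting recorded | Profile item 3 | Primary-care types only |

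Aim 1, the recipients and item 1 are compatible with a survey of both sectors. The introduction and profile item 3 are compatible only with a survey of primary care. The two groups need to be reconciled.

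**Step 2. Can the form identify the EPR described?** No item asks. Profession and centre name help in part. A doctor or nurse who ticks a primary-care profession is probably describing a primary-care system. A specialist is not necessarily hospital-based, *other* is undefined, and some systems may be shared between sectors. Some replies would stay unclassifiable.

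**Step 3. What mixing can do.** Let h be the share of replies that describe hospital EPRs, a the frequency of a given field in those systems, and b its frequency in primary-care systems. The pooled frequency is

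h·a + (1 − h)·b,

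which differs from b by h·(a − b). None of h, a or b is in the documents. The difference is zero if a = b, and its sign depends on which is larger. Neither size nor direction can be stated.

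**Step 4. What a missing *don't know* can do.** Let p be the true frequency and d the share of respondents who do not know, with knowledge assumed unrelated to presence.

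- All unsure respondents tick NO: the reported frequency is p·(1 − d), which is too low.
- They guess evenly: it is p·(1 − d) + d/2, which is pulled towards one half.
- They leave the item blank: the frequency among those who answered is p, but a blank for not knowing looks the same as a skipped item.

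Again d is not given, and the documents do not say which behaviour to expect.

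**Step 5. Is not knowing realistic?** Protocol section 5, Intervention, says that in Catalonia administrative staff collect country of origin, age and sex, and that in Andalusia the data sit in a central user database. The survey goes to clinicians. In these two settings at least, the respondent may not see how or whether a field is filled. The first behaviour in step 4 would also lean towards the sub-study's own premise, in its Justification, that country of origin is seldom part of routine data.

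**Step 6. Does the analysis repair this?** Sub-study section 5 does not restrict or stratify by setting, does not say that profession or centre name will be used to classify replies, and has no rule for blanks or uncertain answers.

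**The case against.** The strongest reply is that the sub-study includes specialists on purpose and that Aim 1 is not confined to primary care. On that reading hospital answers are wanted, and only the questionnaire's introduction is out of line. This stands as far as it goes: hospital answers are not errors against Aim 1. It does not remove the problem, because under either target a pooled figure that cannot be assigned to a type of system is hard to interpret.

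Second, profession and centre name allow some separation, and nothing says the items are mandatory, so an unsure respondent may be able to skip or comment in item 9. Both points stand. They limit the harm but leave a residue that the plan does not address.

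Third, this is a two-minute descriptive survey aimed at an inventory of indicators, and no percentage for primary-care systems is promised. That is fair and sets the weight of the point.

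A reader might go further and infer that hospital systems and guesses will be counted as primary-care facts, or that a comparison with the focus groups is compromised. The documents support neither. No text pools specialists into a primary-care figure. The focus groups serve a different aim, migrants' perceptions in Catalonia, and no comparison between the two sources is planned.

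**Conclusion.** The point holds as a risk that the plan leaves open. The scope is stated in two incompatible ways, the form does not record which EPR is described, and it cannot separate an informed NO from a lack of knowledge. Hospital and primary-care answers may be mixed, and uncertainty may appear as NO or as a blank.

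The size cannot be estimated from the documents, and any percentage put on it would be assumption throughout. The conclusion rests on two assumptions: that some specialists who reply work with hospital EPRs, and that some respondents do not know how their system registers origin.

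This is a minor point. It concerns one sub-study survey and does not touch the trial's primary outcome, sample size or difference-in-differences analysis.

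**What to change.** 1. **Reconcile the target.** State the same scope in sub-study section 3 (Aim 1), section 4 (stage II) and the questionnaire introduction: primary care only, or primary care and hospitals. The documents do not settle which is meant.
2. **Setting.** Add *Hospital* and *Other* to profile item 3 and drop the primary-care restriction from its heading.
3. **System described.** Add one item before item 2: do the answers describe a primary-care EPR, a hospital EPR, or one shared by both?
4. **Uncertainty.** Add *Don't know* to items 2, 3, 4 and 6. Item 1 hardly needs it, since respondents should know whether their own workplace has an EPR.
5. **Analysis.** State in sub-study section 5 that results are reported separately by EPR type and that the *don't know* share is shown for each item.
6. **Replies already collected.** Split them by profession and centre name, and report the share that cannot be classified.

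The cost is a slightly longer form and smaller denominators per setting.

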AST Aspartate Aminotransferase
ALT Alanine Aminotransferase

GGT Gamma-Glutamyl Transpeptidase
STDs Sexually Transmitted Diseases
ACT Anatomical Therapeutic Chemical

1. Introduction

1.1 Preface

Migration is a significant, complex, and growing global phenomenon of critical importance to European countries¹. Migrants may have particular health needs; they are disproportionately affected by key infections, including tuberculosis (TB), human immunodeficiency virus (HIV), hepatitis B virus (HBV) and hepatitis C virus (HCV) in Europe; and this has been seen associated with the incidence in the country of origin, socio-economic risk factors and other comorbidities on arrival to the host Europe². Similarly, certain imported diseases, only prevalent in migrant populations³⁻⁶, are at risk of transmission in non-endemic areas under special circumstances (through transplants, blood-transfusion or congenitally)⁵ and are potentially severe, particularly if there is a diagnosis delay, in immunosuppressed patients⁶. Finally, female genital mutilation (FGM) is a neglected condition, with estimates about 38000 migrant women in some European countries⁷.

The new guidelines from the European Centre for Disease Control and Prevention⁸ on infectious diseases screening and vaccination in new-arriving migrant populations and alongside country-specific guidelines, promote screening implementation at the primary care (PC) level⁹. In particular, ECDC guidelines call for innovative approaches to multi-disease testing and vaccination in high-risk migrants⁸. With the aim of improving patient care by strengthening medical decisions, there has been an outstanding development of clinical decision support systems (CDSS) in the last decade¹⁰. In such tools, the characteristics of an individual patient are matched to a computerized clinical staff knowledge base in patient-specific assessments and recommendations are then presented in the electronic patient record (EPR) system to the clinical staff for decision. Our research group has already developed an innovative prototype digital software (CRIBMI)¹¹. Data shows the digital tool is feasible to implement, acceptable to healthcare professionals and migrants, and well adapted to the PC setting¹², with data suggesting that the digital tool is improving the diagnosis of imported conditions but also other common communicable diseases in migrants when comparing it with a standard training programme¹².

1.2 Purpose of the analysis

The purpose of this analysis is to evaluate the health impact of the ISMiHealth tool validating the tool in a higher number of primary care centres (PCCs) in Catalonia, Spain; and to explore preliminary effectiveness data of the tool in another healthcare setting, Andalusia, Spain.

2. Study objectives and Endpoints

2.1 Main Study Objectives

'To develop an integrated and PC based, communicable diseases and FGM screening programme for migrant populations in Spain in order to promote better health and integration.'

For this, the research group will evaluate the health impact of the ISMiHealth tool in the site of Catalonia, while preliminary effectiveness data will be evaluated in the site of Andalusia.

2.2 Specific Study Objectives

Primary objective 1: To compare the detection rate per month of all aggregated infections (HIV, HBV, HCV, TB, *T.cruzi*, *S.stercoralis* and *Schistosma spp.* infections) between the intervention and control centres over at least five years until the end of the intervention. In the Andalusian site, syphilis, latent TB and intestinal parasites will also be included.

Secondary objective 2: To compare the detection rate per month of each individual condition, the infections and FGM cases, between the intervention and control centres over at least five years until the end of the intervention.

Secondary objective 3: To compare the number of early HIV diagnoses between the intervention and control centres over at least five years until the end of the intervention.

Secondary objective 4: To compare the number of early HBV and HCV diagnoses between the intervention and control centres over at least five years until the end of the intervention.

Secondary objective 5: To compare the number of screening tests performed for all aggregated infections between the intervention and control centres over at least five years until the end of the intervention.

Secondary objective 6: To compare the number of screening tests performed for each individual condition between the intervention and control centres over at least five years until the end of the intervention.

Secondary objective 7: To estimate associations between the screening performance of all aggregated infections with different socio-demographic and epidemiological factors.

Secondary objective 8: To estimate associations between the screening performance of each individual condition with different socio-demographic and epidemiological factors.

Secondary objective 9: To measure the number of the diagnosed individuals with follow-up visits in the hospital of reference.

Secondary objective 10: To measure the number of the diagnosed individuals that have received treatment.

Secondary objective 11: To estimate the prevalence of each infection and FGM in the migrant population.

